PROTOCOL SYNOPSIS

A Phase 2 Randomized, Double-Blind, Placebo-controlled Study to Evaluate the Effects of Two Doses of MEDI6012 on Apolipoprotein B100 Metabolism in Subjects with Stable Atherosclerotic Cardiovascular Disease.

Principal Investigators:

[name]

Co-Investigator(s):

[name] [name]

Version History:

Version 1. 3/2018

Version 2. 5/2018

Version 3, 7/2018

Version 4. 8/2018

Version 5. 9/2018

Version 6. 10/2018

Version 7. 11/2018

Version 8, 7/2019

Study site(s) and number of subjects planned

Columbia University Medical Center

[name]

This is a single site study that will enroll a maximum of 8 subjects.

Study period		Phase of development
Estimated date of first subject enrolled	12/15/2018	Phase 2
Estimated date of last subject completed	11/30/2019	

1

I. Study design

This is a Phase 2, single-center, placebo controlled, double-blind, randomized crossover study to determine the effects of MEDI6012 on the metabolism of apolipoprotein B100 (apoB100) lipoproteins in individuals with stable atherosclerotic cardiovascular disease (ASCVD). Studies will use stable isotope to determine the *in vivo* kinetics of apoB100 in VLDL, IDL, and LDL as well as VLDL TG. The primary outcome will be the percent difference in the fractional clearance rate (FCR) of LDL apoB100 on treatment with MEDI6012 versus on treatment with placebo. FCR is defined as the percent of the circulating pool of LDL apoB100 cleared from the plasma each day. At least 8 subjects will be randomized at Columbia University Medical Center to evaluate the effect of an IV push dosing regimen that includes a loading dose of 300 mg MEDI6012 followed by a 150 mg maintenance dose of MEDI6012 at 48 hours.

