Once consented, subjects will undergo a screening period of up to 28±4 days. For subjects requiring a washout of dyslipidemia medication other than a statin or ezetimibe, or supplement, a 56±2day screening period is allowed (with repeat screening safety and lipids labs within 28±4 days of enrollment). Once enrolled and randomized, subjects will be instructed in an AHA heart healthy diet and stay on that diet, with frequent follow-up telephone calls to obtain diet histories and to reinforce the diet over two weeks before inpatient visit. They will then be admitted to the inpatient research unit of the Irving Institute for Clinical and Translational Research. On day 0, they will arrive in the morning and have fasting blood samples. The first dose of either active drug or placebo will be administered by IV push in the morning hours. They will be observed for the next 2 hrs. for immediate IP reactions and then discharged home with guidelines to continue to follow an AHA Heart Healthy Diet. They will return to our center at 12pm the next day (Day 1-post first dose) and be admitted to our unit for 2 nights. At the time of admission, stat safety bloods will be drawn to ensure no adverse effects from first IP administration. They will be provided with lunch and dinner but will be NPO after 8pm. At 1am (or 8 hrs before the stable isotope administrations) (Day 2) they will start liquid feedings (q2hrs) as part of a protocol obtaining a nutritional steady state before the start of stable isotope administration and kinetic studies. The composition of this liquid formula is 57% carbohydrate, 18% fat, and 25% protein. They will receive the 2nd dose of either active drug or placebo on the morning of Day 2 (exactly 48 hrs. from Day 0 administration). One hour after the second dose (Day 2-9am), a preisotope administration blood draw will be obtained (0hr). Immediately after blood draw stable isotopes will be administered to subjects for the study of lipid and lipoprotein kinetics, and 17 timed blood samples (see procedure schedule) will be obtained for the next 24 hr. followed by discharge. Subjects will repeat this same protocol 6-8 weeks later but will receive the alternative treatment. In the period between the first and second studies, subjects will be monitored and re-instructed as needed in the AHA diet. Two nutritional assessments via 24 hr. recalls will ensure that all subjects maintain a constant healthy lifestyle during the washout period between each study. All subjects will have a 'safety' visit 28±4 days after the first study period. A blood sample will be obtained to ensure that the subject's plasma lipid levels are the same as those during the first study. If they differ significantly, intensive diet and lifestyle counseling will be initiated and continued on a bi-weekly basis for the rest of the inter-study period.

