week wash out between treatments. Thus, subjects will be randomized to receive two doses of placebo or two doses of MEDI6012 at 0 and 48 hours during the first study period and two doses of the other drug during the second study period. Follow up, for safety monitoring, will be performed 28±4 days after the completion of each study period. ADA samples will be obtained at days 0 of inpatient kinetic outcome study and 28±4 days after each study period. If ADA is present at day 28±4days, a second sample will be obtained as soon as possible and if positive, the subject study order will be unblinded and if the subject was on active drug, the study will be stopped, and that subject will have an additional sample for ADA will obtained at day 56±4. Further follow-up for continued presence of ADA is described above on page. A new subject will be enrolled to replace the one with an incomplete study.

VII. STATISTICAL CONSIDERATIONS

Sample Size: This is an exploratory pilot study. We estimate, from prior studies, that administration of MEDI6012, on the background of high potency statin, will reduce LDL apoB (extrapolating from total apoB changes) by 10-15%. If we assume that there will be no change in LDL apoB PR, we can expect a somewhat larger effect size for LDL apoB FCR: about 15-20%. With 8 subjects studied on placebo and then on treatment, there will be statistical significance (p=0.012, two-tailed), by the nonparametric Wilcoxon signed rank test, if all 8 subjects increase their FCRs, regardless of the magnitude and inter-subject variability of the increases. By the parametric paired t-test, there will be statistical significance if the average increase in FCR is equal to or greater than the SD of the change (e.g., >=20% increase when SD=22%, >=15% increase when SD=17%). In our previous studies, the SD of percent change in paired studies has been smaller than the actual percent change. In other words, there will be statistical significance by a paired t-test if the effect size is 1 or greater, which has been the case in our prior studies.

Therefore, we plan to enroll and complete studies on 8 subjects. Drop-outs will be replaced, although we do not, based on a very long and large experience, expect this to occur.

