Statistical Analyses: The primary PD endpoint will be the percent change (and 95% confidence limits) in the FCR of LDL apoB100 during administration of MEDI6012 from the FCR of LDL apoB100 during administration of placebo. The significance of this change will be assessed using either a Wilcoxon Signed Rank test. If the intra-individual variability of change is 17% or less, we can also use a paired t-test at the two-sided alpha level of 0.05.

All PD parameters, including concentrations of lipids and apolipoproteins in isolated lipoproteins, additional lipoprotein kinetic parameters, the concentrations of lipids and apolipoproteins in plasma, and the concentrations and sizes of lipoprotein particles will also be summarized as percentage change (and 95% confidence limits) on active drug versus placebo. Paired t-tests will be used to assess differences, but these will all be exploratory analyses. Plots of the mean and individual subject values will also be provided over time for selected parameters.

VIII. Safety

The safety analysis will be based on the review of descriptive statistics (summary tables) and individual data for adverse events (cases) and clinical laboratory tests. Adverse events will be coded using medical dictionary for regulatory activities (MEDRA), and the number of subjects with treatment-emergent adverse events (TEAEs) will be summarized. Potentially clinically significant abnormalities (PCSAs) for clinical laboratory, vital sign, and ECG data and out-of-normal range values for clinical laboratory data will be flagged and summarized in frequency tables. Results of ADA data will be summarized for each timepoint.

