4. STUDY DESIGN

4.1 Overview

MEDI1062: Kinetics of apoB100 LDL

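### Treatment order is randomised over two periods, but the primary analysis has no period term and the sequence given to a replacement is unstated; a period-adjusted sensitivity estimate is a cheap safeguard

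*Combined protocol and SAP*

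**What the plan says.** Section I of the synopsis describes a "placebo controlled, double-blind, randomized crossover study" and adds: "Subjects will repeat this same protocol 6-8 weeks later but will receive the alternative treatment". Section VI confirms that order is what is randomised: "subjects will be randomized to receive two doses of placebo or two doses of MEDI6012" in the first period, then the other product in the second.

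Section VII, Statistical Analyses, defines the primary endpoint as the percent change in LDL apoB100 FCR on active versus placebo. On testing it says: "The significance of this change will be assessed using either a Wilcoxon Signed Rank test". It continues: "If the intra-individual variability of change is 17% or less, we can also use a paired t-test". Neither test is given a period or sequence term.

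On replacement, section VII says: "Drop-outs will be replaced, although we do not, based on a very long and large experience, expect this to occur". Section 5.7 requires replacement of subjects who withdraw, have incomplete kinetics, or are stopped for ADA in period 1. Neither place says which sequence the new subject receives. Section 5.4 has randomisation in its title but covers consent, identification numbers and screening failures.

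The sample-size paragraph says "With 8 subjects studied on placebo and then on treatment". This reads as a fixed order, but sections I and VI are clear that order is random.

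**The concern.** In a two-period crossover, an active-minus-placebo difference carries any change between periods. It is added for subjects who take placebo first and subtracted for those who take active first. With equal sequences the shift cancels from the mean but stays in the spread of the differences, so the interval widens and power falls. The 17% condition for the t-test is also met less often. With unequal sequences, part of the shift remains in the mean and is reported as a drug effect on FCR.

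The protocol gives some reason to allow for a shift. Period 1 follows about two weeks of diet instruction, whereas period 2 comes 6-8 weeks later, after re-instruction and possibly intensified counselling. Replacement could also unbalance the sequences. Under section VI, the ADA stop after period 1 applies to subjects found to have been on active drug, so it would remove active-first subjects.

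**Working it through.** **Inputs.** From section VII: 8 completers, two-sided alpha 0.05, and effect/SD of change of 15/17 and 20/22 percentage points. (Section 4.2 speaks of at least 6 subjects; 8 is used here.) The period shift *d* (period 2 minus period 1) is not in the documents. It is assumed to be 0, 5, 10 or 15 points.

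**The plan's own figures.** They reproduce.
- Signed-rank with all 8 increasing: W = 36, mean 18, variance 51, so z = 18/√51 = 2.52 and p = 0.012 by normal approximation (exact: 2/256 = 0.008).
- Paired t, 7 df: 20/(22/√8) = 2.57, p = 0.037; 15/(17/√8) = 2.50, p = 0.041.

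**Period-adjusted estimate.** Take half the difference between sequences (placebo-first minus active-first) in the mean period-2 minus period-1 change. The expectations are (effect + d) and (−effect + d), so *d* cancels. SE = (SD/2)·√(1/n₁ + 1/n₂), on 6 df. At 4:4 this equals SD/√8, the paired-t SE, so the only cost is the critical value: 2.447 instead of 2.365. The plan's two examples remain significant (p = 0.042 and 0.047).

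**Equal split, 4:4.** The expected sample variance of the differences becomes SD² + 8d²/7. For SD 17 and d = 10 this is 289 + 114.3 = 403.3, an SD of about 20.1. Simulation, SD 17, effect 15:

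| Shift | Signed-rank power | Paired-t power | Adjusted power | Mean 95% half-width, paired | Half-width, adjusted | P(observed SD ≤ 17) |
|---|---|---|---|---|---|---|
| 0 | 50% | 57% | 55% | 13.7 | 14.1 | 57% |
| 5 | 47% | 54% | 55% | 14.4 | 14.1 | 50% |
| 10 | 36% | 44% | 55% | 16.2 | 14.1 | 33% |
| 15 | 23% | 30% | 55% | 19.0 | 14.1 | 15% |

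At SD 22, effect 20, the pattern is milder. From no shift to a 10-point shift, paired t goes from 60% to 51% and signed-rank from 53% to 44%; adjusted stays at 58%.

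The adjusted t overtakes the paired t on mean squared width when 2.365·√(1 + 8k²/7) = 2.447, with k = d/SD. This gives k = 0.249, or 4.2 points at SD 17 and 5.5 at SD 22.

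**Unequal split.** Bias in the unadjusted mean = d × (placebo-first count − active-first count)/8.

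| Shift | 5:3 | 6:2 |
|---|---|---|
| 5 | 5 × 2/8 = 1.25 | 5 × 4/8 = 2.5 |
| 10 | 10 × 2/8 = 2.5 | 10 × 4/8 = 5.0 |

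With a 10-point shift, SD 17 and no drug effect, type I error (signed-rank / paired t) is 1.9/2.5% at 4:4, 2.7/3.6% at 5:3 and 5.6/7.3% at 6:2.

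Imbalance also costs the adjusted estimate precision: its power at 15/17 is 55% at 4:4, 53% at 5:3 and 44% at 6:2.

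**Over the randomisation.** If order were a simple coin toss (not stated), P(4:4) = 70/256 = 27%, P(5:3) = 112/256 = 44% and P(6:2 or worse) = 74/256 = 29%. Averaged over splits the bias is zero. Simulated type I error for shifts of 0 to 15 points is 3.9% for signed-rank and 5.0-5.2% for paired t.

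**The case against.** The harm is wholly assumed. The documents report no period effect, and section I builds in controls against drift: an interim lipid check against the first study, counselling if lipids differ, two 24-hour diet recalls, and the same timed inpatient formula protocol in both periods. That stands, and it is why the point is a safeguard.

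The gain for the primary test is smaller than the table suggests. Part of the gap between signed-rank and adjusted t is the usual parametric difference, visible at zero shift (50% versus 55%). Against the period-adjusted rank alternative (exact rank-sum test), the signed-rank test loses power only beyond a shift of about 8.8 points at SD 17 and 11.4 at SD 22. That stands too, and it argues for leaving the signed-rank test as primary.

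A log-scale adjusted estimate answers a slightly different question. With a true ratio of 1.15, log SD 0.145 and no shift, the mean percent change is 16.2 while the geometric figure is 15.0. That gap is about the size of the 5:3 bias from a 5-point shift, so it could be misread as a period effect unless the plan says otherwise.

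A ratio or blocking scheme may exist outside the text supplied. Section 4.1 shows only a title line ("MEDI1062: Kinetics of apoB100 LDL"), section 6 points to an appendix table, and a pharmacy list may be held separately. Little weight should therefore go on their absence. The missing period term does not depend on this, because the analysis paragraph is present.

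Imbalance through replacement is also unlikely. Drop-outs are not expected, and section 1.1 reports no treatment-emergent ADA among MEDI6012-treated subjects in the cited multiple-dose study.

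**Conclusion.** The point holds as a cheap improvement to an exploratory 8-subject crossover. The planned tests ignore period, and nothing stated keeps the sequences balanced when a subject is replaced. If a shift exists, the cost at 4:4 is precision: for 10 points at SD 17, 13 points of paired-t power and 14 of signed-rank power. At an unequal split, a quarter (5:3) or half (6:2) of the shift enters the estimate. All of this rests on the assumed shift, normal differences and the plan's SDs.

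A reader might infer more, but the documents do not support it:
- **That the primary test is invalid or inflates type I error.** Error exceeds 5% only after conditioning on 6:2 or worse with a large shift. Over random order it stays close to nominal or below, and at 4:4 it is conservative.
- **That a period effect is present.** None is reported.
- **That there is no replacement rule.** Sections VII and 5.7 give one; only the replacement's sequence is unstated.
- **That placebo always comes first.** The sample-size wording is loose; order is random.

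**What to change.** **Section VII.** Keep the signed-rank test as primary and add a prespecified sensitivity estimate, reported whatever the observed SD: half the difference between sequences (placebo-first minus active-first) in mean period-2 minus period-1 log FCR, pooled variance, t on 6 df, back-transformed with a 95% CI. State that this is a geometric mean ratio, that it will differ somewhat from the mean percent change even with no period effect, and that the gap is not to be read as a period effect.

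**Section 5.4, in support.** State that completers are allocated 4:4 by sequence from a concealed list held by the research pharmacy. State also that the pharmacy assigns replacements to keep balance, without disclosing the block structure, the replacement rule or the replaced subject's sequence to blinded staff.

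**Editorial.** Reword the sample-size sentence to say that each subject is studied on both treatments in random order. The ADA stopping text in sections I, VI and 5.7 differs and must be reconciled separately.

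**Cost.** Wording and a list; no extra subjects or visits, and the planned test is unchanged. With no shift at 4:4, the adjusted interval is about 3% wider than the paired-t interval (mean half-width 14.1 versus 13.7) and its power about 2 points lower (55.2% versus 57.5%). There is one blinding risk: after an ADA unblinding under section VI, staff who know that subject's order could guess a balancing replacement's sequence. If that cannot be contained, the pharmacy can draw the replacement's sequence at random. Should 5:3 result, the adjusted estimate remains unbiased, with 53% power.

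### The paired t-test on the primary endpoint is allowed only under an undefined 17% variability rule that is unsound, and the plan does not say which test decides or which method gives the 95% limits

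*Combined protocol and SAP*

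**What the plan says.** All the relevant statistical text is in section VII, Statistical Considerations, of the synopsis in the combined protocol and SAP.

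- **Endpoint**, under Statistical Analyses: "The primary PD endpoint will be the percent change (and 95% confidence limits) in the FCR of LDL apoB100", on MEDI6012 relative to placebo. No method is given for the limits.
- **Test**, same paragraph: "The significance of this change will be assessed using either a Wilcoxon Signed Rank test". The word *either* has no second alternative in that sentence.
- **Second test**, next sentence: "If the intra-individual variability of change is 17% or less, we can also use a paired t-test at the two-sided alpha level of 0.05".
- **Sample Size**, on the Wilcoxon test: "there will be statistical significance (p=0.012, two-tailed), by the nonparametric Wilcoxon signed rank test, if all 8 subjects increase their FCRs", and this holds "regardless of the magnitude and inter-subject variability of the increases".
- **Sample Size**, on the paired t-test: significance is expected when the mean increase is "equal to or greater than the SD of the change (e.g., >=20% increase when SD=22%, >=15% increase when SD=17" (per cent). Past experience is offered in support: "In our previous studies, the SD of percent change in paired studies has been smaller than the actual percent change".

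Section I, Study design, makes this a two-period crossover: "Subjects will repeat this same protocol 6-8 weeks later but will receive the alternative treatment". Sections 3.1 and 4.2 restate the endpoint or primary outcome without naming a test.

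**The concern.** Three things look wrong.

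1. **The condition has no definition.** Each subject has one placebo study and one active study, hence one change. Variability of change within an individual cannot be estimated from one change. The Sample Size paragraph speaks instead of the SD of the change across subjects, and uses 17% as an example of it. That is the most plausible source of the rule, but the plan does not say so. Nor does it say whether the 17% is to be checked on this trial's data.
2. **The condition does no statistical work.** A paired t-test divides by the SD already. What it needs is approximate normality of the changes, and a small SD does not supply that.
3. **Two tests of one endpoint, with no rule between them.** If they differ, the plan does not say which p-value decides. It also leaves open whether the 95% limits come from the t distribution or from the signed ranks.

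At stake is how clearly the trial's one primary result is specified, with some room to choose the test after seeing the data.

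**Working it through.** **Inputs from section VII:** n=8 pairs; examples of a 15% increase with SD 17% and a 20% increase with SD 22%; two-sided alpha 0.05; Wilcoxon p=0.012 if all 8 increase. **Assumptions:** normally distributed percent changes, and the 17% rule applied to the sample SD of the change.

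**1. The plan's Wilcoxon figure.** With 8 of 8 increases the rank sum is 36. Its null mean is 18 and its variance is 8×9×17/24 = 51.

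- Normal approximation without continuity correction: z = (36−18)/√51 = 2.52, p=0.0117. This reproduces the stated 0.012.
- Exact: 2/256 = 0.0078.

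The stated value is conservative for that one outcome. As a 5% test the approximation is not:

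| Smaller rank sum | Exact p | Approximate p |
|---|---|---|
| 0 | 0.0078 | 0.0117 |
| 3 | 10/256 = 0.0391 | 0.0357 |
| 4 | 14/256 = 0.0547 | 0.04995 |

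The exact test rejects up to a rank sum of 3, a true level of 3.9%. The approximation also rejects at 4, a true level of 14/256 = 5.5%.

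**2. The plan's t-test examples** (7 df, t = mean/(SD/√8)).

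- 15%/17%: t = 15/6.01 = 2.50, p=0.041.
- 20%/22%: t = 20/7.78 = 2.57, p=0.037.

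Both are significant, as the plan says. The second has an SD above 17%, so the rule would not allow the test that the Sample Size paragraph uses it to illustrate.

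**3. How often the rule is met.** P(sample SD ≤ 17) = P(χ²₇ ≤ 7×(17/σ)²).

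- True SD 17%: P(χ²₇ ≤ 7.00) = 57%.
- True SD 22%: P(χ²₇ ≤ 4.18) = 24%.

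**4. The tests can disagree when the rule is met.** Two constructed sets of eight percent changes:

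| Changes | SD | t-test p (95% CI) | Exact Wilcoxon p (interval) |
|---|---|---|---|
| 10, 12, 14, 16, 18, 20, 22, −15 | 11.7 | 0.022 (2.4 to 21.9) | 0.055 (−0.5 to 20.0) |
| 3, 4, 5, 6, 7, 8, 9, 45 | 13.9 | 0.063 (−0.8 to 22.5) | 0.008 (4.0 to 26.0) |

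In the first set the version of the Wilcoxon test also matters: the rank sum is 4, so the approximation gives 0.04995.

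**5. How often that happens (simulation).** Share of all trials in which the rule is met and the tests disagree:

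| True mean/SD | Exact Wilcoxon | Approximation |
|---|---|---|
| 15%/17% | 4.5% (t-test alone significant in 4.0%) | 2.8% |
| 20%/22% | 1.2% (t-test alone significant in 1.1%) | 0.7% |

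**6. False-positive rate if either test may be claimed.** Over true SDs from 10% to 25%, the maximum is 5.3% with the exact Wilcoxon test (3.9% alone) and 6.0% with the approximation (5.5% alone).

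**7. Coverage if the t interval were reported only when the rule is met.** Integrating over the χ²₇ density below the cut-off gives 91.8% at true SD 17% and 85.6% at 22%. In the same trials the signed-rank interval covers 93.6% and 88.4%, so the loss comes from selecting trials with a low SD, not from the t method. An interval reported whatever the SD covers 95%.

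**The case against.** The best defence is that the plan does have a default. The Wilcoxon test is prescribed without condition, the t-test is only permitted as an addition, and the Sample Size paragraph also takes the Wilcoxon test first. The stray *either* is an editing slip. This stands: a reader might infer that the primary p-value cannot be identified at all, and the text does not support that. What is missing is a statement of which test decides if both are run and differ.

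A second defence is that 17% was never meant as a validity condition. With n=8 a mean of 0.836×17% = 14.2% is significant, so an SD of 17% is roughly where the lower expected effect, 15%, just passes. That may explain the number. It does not justify a rule on when the test may be used, since a larger SD already makes the t-test harder to pass.

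Three stronger readings are tempting and should be resisted.

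- A reader might take the 17% as a per-measurement SD, which would correspond to a larger SD of change. Nothing in the documents supports this, whereas the Sample Size paragraph gives 17% as an SD of change.
- A reader might conclude that the primary 95% interval under-covers. The plan attaches the condition to the test only and promises the limits without condition, so the step 7 figures apply only if the interval is gated as well.
- A reader might conclude that error control is lost. Step 6 shows that it is not, and the plan calls the trial an exploratory pilot.

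**Conclusion.** The point holds as a defect of specification with a small numerical effect. The 17% rule is undefined, is not a condition that a t-test needs, conflicts on its likeliest meaning with the plan's own 20%/22% example, and gives a second chance at significance with no statement of which test or interval is primary. The trial's exploratory status lowers the stakes but does not remove the point: the plan labels its paired t-tests of the PD parameters generally as exploratory, while this endpoint is named primary and has its own 0.05 level.

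The sizes in steps 5 and 6 rest on normal changes and on checking the rule against trial data. If the 17% was meant to be judged from previous studies, no selection on trial data occurs, but the choice between tests stays open. The p=0.012 does not mislead about 8 of 8 increases, which is significant either way. It matters because it points to an approximation whose true level at n=8 is 5.5%. The change is worth making because it is cheap and settles the primary result in advance.

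**What to change.** In section VII, Statistical Analyses:

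1. Delete *either* and the 17% condition.
2. Keep the Wilcoxon signed rank test as the single primary test, stated as exact and two-sided at 0.05.
3. Report the Hodges-Lehmann estimate with its matching interval: the 4th smallest and 4th largest of the 36 Walsh averages, with exact coverage 1 − 10/256 = 96.1%.
4. Report the paired t-test and its 95% interval as a sensitivity analysis, whatever the SD.

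In Sample Size, restate p=0.012 as the exact 0.0078.

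**Cost:** two or three sentences, with no change to data collection. The exact Wilcoxon test has a true level of 3.9% and about 7 points less power than the t-test: 50.5% against 57.5% at 15%/17%, and 52.9% against 60.0% at 20%/22%. Naming the paired t-test with its t interval as the single primary analysis would cure the defect equally well and keep that power, at the price of relying on approximate normality of 8 percent changes.
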